6.1. Efficacy Endpoint(s)

Primary

- *Cumulative confirmed MCyR defined as Complete Cytogenetic Response (CCyR) or Partial Cytogenetic Response (PCyR) by 1 year (52 weeks) in 2nd and 3rd line CP patients.*
- *Cumulative confirmed MCyR by 1 year (52 weeks) in 4th and later line CP patients.*
- *Cumulative confirmed OHR defined as Complete Hematological Response (CHR) or Return to Chronic Phase (RCP) by 1 year (52 weeks) in AP and BP patients.*

The local cytogenetic assessments will be used for the primary endpoint analysis in CP patients. The local hematologic assessments will be used for the primary endpoint analysis in AP and BP patients.

Cumulative response is any response on-treatment up through Week 52 (based on the date of assessment) with a 4 week window (\leq Week 56). Response is confirmed for cytogenetic and hematologic with 2 consecutive responses at least 28 days apart. The date of confirmed response is the date of the first response. Cytogenetic and hematologic responses are defined in [Appendix 2](#) and [Appendix 1](#). MCyR is defined as a CCyR or PCyR. OHR is defined as CHR or RCP. To be considered a responder, the patient must have maintenance of baseline response for \geq 5 weeks for hematologic response or \geq 52 weeks for cytogenetic response or an improvement from baseline. Patients with PCyR at baseline must attain CCyR on-treatment to be counted as a cytogenetic responder. Patients with at least MMR and a deeper molecular response than baseline are counted as confirmed CCyR.

Secondary

- *Cumulative MCyR in CP, AP and BP patients.*
- *Cumulative confirmed OHR in AP and BP patients by line of therapy.*
- *Cumulative best response in CP, AP, and BP patients.*
- *MCyR at 3, 6, 12, 18, and 24 months in CP, AP, and BP patients.*
- *Confirmed OHR at 3, 6, 9, 12, 18, and 24 months in AP and BP patients.*
- *Cumulative confirmed CHR.*
- *Cumulative MMR in CP, AP, and BP patients.*
- *Duration of CCyR.*
- *Duration of MMR.*

The local cytogenetic assessments will be used for the secondary endpoint analyses for all patients. The local hematologic assessments will be used for the secondary endpoint analyses for all patients. *Molecular assessments will be performed at a central laboratory. Endpoint analysis for molecular response will be carried out by independent central analysis.*

Cumulative response is any response on-treatment. Landmark “at” responses need to occur within a 2 week window of the landmark for those before Week 39 and within a 4 week window for Week 39 and after (eg, Month 3 is \geq Week 11 to \leq Week 15, Month 18 is \geq Week 74 to \leq Week 82, etc.). Molecular responses are defined in [Appendix 2](#). Response is unconfirmed for cytogenetic and molecular and confirmed for hematologic with 2 consecutive responses at least 28 days apart. The date of hematologic confirmed response is the date of the first response. To be considered a responder, the patient must have maintenance of baseline response while on-treatment or an improvement from baseline. The hierarchy to assess for best response from best to worst is \geq 4.5-log reduction of BCR-ABL transcripts from standardized baseline on the international scale (MR^{4.5}), MR⁴ (\geq 4-log reduction), MMR (\geq 3-log reduction, same as MR³), CCyR, PCyR, CHR, and OHR.

Duration of response (DOR) for CCyR and MMR, is defined as the time from first response to confirmed loss, progression of disease as assessed by the investigator, or on-treatment death due to any cause ([date of loss – date of first response + 1]/30.4). For CCyR, confirmed loss is defined as 2 consecutive assessments with >0 Ph+ metaphases at least 28 days apart. For MMR, confirmed loss is defined as 2 consecutive assessments at least 28 days apart with a <3 -log ($>0.1\%$) reduction in transcripts from standardized baseline one of which corresponds to a \leq 2-log reduction ($\geq 1\%$). The date of confirmed loss is the earlier of first loss, progression, or death date. Patients without confirmed loss, progression, or death are censored at the last valid assessment where response could be assessed.

Exploratory

- *PFS.*
- *OS.*
- *Presence of BCR-ABL mutations.*
- *For Ph- CML patients, cumulative best response (OHR and MMR) anytime on treatment.*
- *Patient reported outcome (PRO) endpoints as measured by Functional Assessment of Cancer Therapy-Leukemia (FACT-Leu).*
- *To collect banked biospecimens for exploratory research, unless prohibited by local regulations or ethics committee decision. Collection of banked biospecimens unless prohibited by local regulations or ethics committee decision. Additional information on collection and potential use is provided in the Banked Biospecimens section.*

- Time to MMR, MR⁴, MR^{4.5}, CCyR, and MCyR.
- Duration of MR⁴ and MCyR.
- Time to confirmed transformation on-treatment.

The local cytogenetic assessments will be used for the exploratory endpoint analyses for all patients. The local hematologic assessments will be used for the exploratory endpoint analyses for all patients. *Molecular assessments will be performed at a central laboratory. Endpoint analysis for molecular response will be carried out by independent central analysis.*

Time to response is the time from first dose to first response, unconfirmed for molecular and cytogenetic ([date of first response – first dose date +1]/30.4). Patients without events are censored at the last molecular or cytogenetic assessment where response could be assessed for the respective endpoint.

DOR for MCyR follows the same rules as the secondary endpoint of DOR for CCyR. DOR for MR follows the same rules as the secondary endpoint of DOR for MMR except confirmed loss is defined as 2 consecutive assessments at least 28 days apart with a <4-log (>0.01%) reduction in transcripts from standardized baseline one of which corresponds to a \leq 3-log reduction (\geq 0.1%).

PFS is defined as the time from first dose to objective progression or relapse as assessed by the investigator and noted as the reason for permanent treatment discontinuation on the case report form (CRF) or on-treatment death due to any cause ([date of progression – first dose date +1]/30.4). Patients without events are censored at the last cytogenetic, hematologic, or laboratory assessment where progression could be assessed. Progression is defined as:

- *For CP, at least one of the following criteria:*
 - *Development of AP or BP CML;*
 - *Loss of CHR (in absence of cytogenetic response) confirmed by 2 complete blood counts (CBC) at least 2 weeks apart; Loss of CHR is defined as:*
 - *WBC count that rises to $>20.0 \times 10^9/L$;*
 - *Platelet count that rises to $\geq 600 \times 10^9/L$;*
 - *Appearance of extramedullary disease not present at baseline including hepatosplenomegaly by palpation or other extramedullary involvement proven by biopsy;*
 - *Appearance of $\geq 5\%$ myelocytes + metamyelocytes in the peripheral blood or appearance of blasts or promyelocytes in the peripheral blood;*
 - *Loss of MCyR (loss of CCyR or loss of PCyR);*

- *Increasing white blood count (WBC) in a patient without CHR, defined as doubling of WBC, to $>20 \times 10^9/L$ on 2 occasions at least 2 weeks apart (after the first 4 weeks of treatment).*
- *For AP, at least one of the following criteria:*
 - *Development of confirmed BP;*
 - *Loss of previous hematologic response over a 2-week period;*
 - *Loss of CHR is defined as:*
 - *WBC count that rises to $>20.0 \times 10^9/L$;*
 - *Platelet count that rises to $\geq 600 \times 10^9/L$;*
 - *Appearance of extramedullary disease not present at baseline including hepatosplenomegaly by palpation or other extramedullary involvement proven by biopsy;*
 - *Appearance of $\geq 5\%$ myelocytes + metamyelocytes in the peripheral blood or appearance of blasts or promyelocytes in the peripheral blood.*
 - *No decrease from baseline levels (if considered clinically relevant) in percentage blasts in peripheral blood or bone marrow on all assessments over a 4-week period.*
- *For BP (of any phenotype):*
 - *Increasing blasts (if considered clinically relevant) peripheral blood or bone marrow over a 4-week period.*

For DOR and PFS, if there is an unacceptable gap between the date of progression or death and the date of the most recent prior disease assessment (>52 weeks), the event will not be used and censorship will be at the most recent prior assessment.

Time to on-treatment transformation, defined by the first progression bullet above, is the time from first dose to confirmed transformation ([date of transformation – first dose date +1]/30.4). Confirmed transformation is defined as 2 consecutive assessments at least 1 week apart or 1 assessment confirmed by progression of disease or death due to any cause. The date of confirmed transformation is the date of the first transformation. Patients without events are censored at the last hematologic or extramedullary assessment where transformation could be assessed.

BCR-ABL mutational status at baseline and treatment discontinuation will be assessed. Emergent mutations are defined as those mutations which were not present at baseline. Patients who were not assessed for baseline mutations are not assessable for emergent mutations.

OS is defined as the time from first dose to the date of death ([date of death – first dose date +1]/30.4). Patients who have not died will be censored at the last known alive date.

For Ph- CML patients, cumulative best response anytime on treatment will be provided. The hierarchy to assess for best response is MR^{4,5}, MR⁴, MMR, MR² (≥ 2 -log reduction), MR¹ (≥ 1 -log reduction), CHR, and OHR.

PRO endpoints are defined in the outcomes research section.

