- Bone marrow aspirate must be collected for local conventional cytogenetic assessment (with at least 20 metaphases). Percentage (%) of Ph+ metaphases, as well as any other chromosomal abnormalities, will be documented. Conventional cytogenetic assessment should be continued until MMR. Only chromosome banding analysis of marrow cell metaphases can be used to assess the degree of CyR (with at least 20 metaphases analyzed). Upon achieving CCyR by the conventional cytogenetic assessment, FISH of blood interphase nuclei with an appropriate probe (Dual-Color Dual-Fusion or Dual-Fusion FISH) could substitute for chromosome

banding analysis of marrow cell metaphases for the assessment of maintenance of the CCyR (which is then defined by <1% BCR-ABL1-positive nuclei of at least 200 nuclei) until MMR is reached. Loss of CCyR using FISH requires resumption of bone marrow conventional cytogenetic assessment (unless the CML disease status is proven to be MMR by qRT-PCR);

- Bone marrow aspirate for morphology (% bone marrow differential) and conventional cytogenetic assessment is required for all patients at the time of suspected progression and/or failure.

Note: in Ph-CML patients, conventional cytogenetic assessment (to detect other potential cytogenetic abnormalities) and molecular cytogenetic assessments using FISH are required at the time of suspected progression and/or failure;

- qRT-PCR for molecular response assessment (BCR-ABL fusion transcript levels) and mutational analysis of the BCR-ABL kinase domain will be performed by a central laboratory. For CP CML, the assessments will be performed using peripheral blood sample. For Advanced Phase (AP and BP) CML, the assessments will be performed using peripheral blood and/or bone marrow samples; mutational analysis will be performed from the peripheral blood or bone marrow samples that were used for molecular response assessment. Loss of confirmed MMR requires resumption of conventional cytogenetic assessment;
- Hematology panel ([Appendix 9](#)); complete hematological assessment response;
- Liver function tests ([Appendix 9](#));
- Chemistry panel; including HbA1C, cholesterol, HDL, LDL, potassium, and magnesium, if clinically indicated ([Appendix 9](#));
- Coagulation tests ([Appendix 9](#));
- Urine or serum pregnancy test ([Appendix 9](#));

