7.1.1.1. Cytogenetic Response Assessment

Cytogenetic analysis will be performed by conventional cytogenetics from bone marrow, requiring at least 20 metaphases in order to evaluate number of Ph+ cells to determine cytogenetic response. Conventional cytogenetic assessment will be performed at scheduled visits until MMR is observed.

Only chromosome banding analysis of marrow cell metaphases will be used to assess the degree of CyR. Upon achieving CCyR by the conventional cytogenetic assessment, FISH of blood interphase nuclei with an appropriate probe (Dual-Color Dual-Fusion or Dual-Fusion FISH) could substitute for chromosome banding analysis of marrow cell metaphases for the assessment of maintenance of the CCyR (which is then defined by <1% BCR-ABL1-positive nuclei of at least 200 nuclei) until MMR is reached. Loss of CCyR using FISH will require resumption of bone marrow conventional cytogenetic assessment (unless the CML disease status is proven to be MMR by qRT-PCR).

For Ph- CML patients, conventional cytogenetic analysis will be performed only at screening and at the time of suspected progression and/or failure. Conventional cytogenetic assessment will be used to detect other potential cytogenetic abnormalities and molecular cytogenetic assessment (FISH) will be used to detect cryptic/variant translocations. Cytogenetic analysis will be conducted locally. Note: The cytogenetic assessment needs to be repeated at least 28 days later to confirm CCyR CML disease status for Ph+ CML patients (when the cytogenetic response is first observed in the absence of MMR, e.g. once CCyR is achieved by G-banding,

FISH is needed to confirm the achievement/maintenance of CCyR at least 28 days later). Loss of cytogenetic response must be confirmed by 2 assessments at least 4 weeks apart. (Note: if confirmation is lacking and the patient goes off treatment due to progressive disease, the assumption is that loss of cytogenetic response (CyR) is confirmed for this study; therefore, the confirmation of loss of CyR 4 weeks apart is not required in this clinical context).

Karyotypic abnormalities in Ph- subclones should be recorded. See [Appendix 11](#) for CyR criteria definitions.

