Handling of missing/incomplete patient local cytogenetic data will be done by the following procedure: for baseline visits, only bone marrow information with ≥ 20 metaphases will be used, otherwise the baseline response will be set to missing. For post-baseline visits, bone marrow information with 20 to 99 metaphases will be used over FISH information with at least 200 nuclei at a specific visit. FISH will only be used to assess CCyR. No conventional bone marrow cytogenetic assessment will be derived when ≥ 100 cells are reported as analyzed for Philadelphia chromosome as this will be considered an error in data entry. If on-treatment molecular monitoring is performed in lieu of conventional cytogenetics or FISH, CCyR may be imputed on a specific date if a MMR is achieved on that date. The results of conventional cytogenetic testing, FISH with ≥ 200 nuclei or banding with ≥ 20 metaphases, will be used in preference to molecular testing, provided they are available and performed on the same date.

Handling of missing/mismatched patient hematologic efficacy data will be done using the following procedure: for each patient, the observations will be sorted by visit and the relative day to first dose.

First, for each observation, peripheral blood and/or bone marrow differentials should add up to 100%. Some sites may not record 0% to reflect uncounted cell types as instructed. Instead, the corresponding field may appear as missing or “ND” even though data collection procedures have been vigorously followed. Also, the differentials may not exactly add up to 100%. To correct this problem, each domain of the differentials will be summed together. If the total is between 98.5% and 101%, the missing values are assigned 0%. Otherwise, the observation is left as is and the record is also to be reported as a data issue.

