Appendix 2. DEFINITIONS OF HEMATOLOGIC, CYTOGENETIC, AND MOLECULAR RESPONSE

Response by Type	Definitions
Hematologic Complete (CHR)	WBC <10 x 10⁹/L Peripheral Blood Basophils <5% No Peripheral Blood myelocytes, promyelocytes, myeloblasts in the differential Platelet count <450 x 10⁹/L Spleen nonpalpable
Cytogenetic * Complete (CCyR) Partial (PCyR) Minor (mCyR) Minimal (minCyR) None (noCyR)	No Ph+ metaphases 1% to 35% Ph+ metaphases 36% to 65% Ph+ metaphases 66% to 95% Ph+ metaphases >95% Ph+ metaphases
Molecular Deep Molecular Response (MR4, MR4.5)	MR4= either (i) detectable disease with <0.01% BCR-ABL1^{IS} or (ii) undetectable disease in cDNA with >10 000 ABL1 transcripts MR4.5 =either (i) detectable disease with < 0.0032% BCR-ABL1^{IS} or (ii) undetectable disease in cDNA with >32,000 ABL1 transcripts in the same volume of cDNA used to test for BCR-ABL1. Ratio of BCR-ABL^{IS} ≤0.1%**.
Major (MMR)	

Abbreviations: CHR, complete hematologic response; CCyR, complete cytogenetic response, PCyR, partial cytogenetic response; Ph+, Philadelphia Chromosome positive; MCyR, major cytogenetic response; mCyR, minor cytogenetic response; minCyR, minimal cytogenetic response; noCyR, no cytogenetic response; MR4, MR4.5, deep molecular response; MMR, major molecular response.

*If bone marrow metaphases cannot be obtained or evaluated by chromosome banding analysis, the definition of CCyR (defined as <1% for FISH) may be based on interphase FISH of blood cells, provided that it is performed with Dual-Color Dual-Fusion or Dual-Fusion FISH probes and at least 200 nuclei are scored.

PCyR and CCyR are counted together and reported as MCyR.

**With ≥5,000 ABL1 transcripts.

Definitions of Hematologic Response for AP and BP CML*

CHR**	WBC \leq institutional upper limit of normal (ULN) ANC \geq 1.0 x 10⁹/L Platelet count \geq 100 x 10⁹/L BM Blasts \leq 5%*** No peripheral blood blasts or promyelocytes; Peripheral blood myelocytes + metamyelocytes $<$ 5%; Basophils in peripheral blood $<$ 5%* No evidence of extramedullary involvement
--------------	---

*The maximum % of basophils in peripheral blood was modified from <2 to $<5\%$ for a less restrictive constraint and alignment with the CHR criteria for CP CML patients according to ELN guidelines.

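### The SAP's rule for confirmed loss of CCyR has no FISH criterion, although CCyR may be followed by blood FISH, so duration of CCyR can be overstated

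*SAP*

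**What the plan says.** SAP 6.1 (secondary endpoints) measures duration of CCyR from first response to confirmed loss, "progression of disease as assessed by the investigator, or on-treatment death due to any cause". Confirmed loss is defined in one sentence: "For CCyR, confirmed loss is defined as 2 consecutive assessments with >0 Ph+ metaphases at least 28 days apart". On dating it says: "The date of confirmed loss is the earlier of first loss, progression, or death date". On censoring: "Patients without confirmed loss, progression, or death are censored at the last valid assessment where response could be assessed".

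Protocol 6.2 and 7.1.1.1 allow another test for the same response. Once CCyR has been reached by banding, interphase FISH on blood (CCyR meaning under 1% positive of at least 200 nuclei) may replace marrow banding until MMR. The protocol recognises that FISH can show loss: "Loss of CCyR using FISH requires resumption of bone marrow conventional cytogenetic assessment". It excepts patients proven to be in MMR and sets no time limit for the marrow. Protocol 7.1.1.1 then states: "Loss of cytogenetic response must be confirmed by 2 assessments at least 4 weeks apart". It does not name the test, and it treats loss as confirmed when the patient goes off treatment for progressive disease.

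The SAP accepts FISH as evidence for the response. Section 7 says "FISH will only be used to assess CCyR", and Appendix 2 says that when marrow metaphases are not obtainable or evaluable, "the definition of CCyR (defined as <1% for FISH) may be based on interphase FISH of blood cells".

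**The concern.** Interphase FISH counts nuclei and cannot report Ph+ metaphases. Read literally, the SAP lets FISH show that CCyR is kept but never that it has been lost, either as the first or as the confirming assessment. A patient with a positive FISH followed by a Ph+ marrow at least 28 days later has two assessments showing loss, yet the SAP counts only one. A second marrow is needed, and the loss takes the date of the first marrow.

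Duration of CCyR is a secondary endpoint. The study is descriptive, so no test is affected, but the reported durations and yearly retention rates would be.

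**Working it through.** **The plan's own figures.** The documents give no loss rate, event count or precision for duration of CCyR. The only planning figure is the maximum standard deviation in Protocol 9.1: sqrt(0.25/45) = 0.0745, which rounds to the stated 0.075. It does not bear on this endpoint.

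**Step 1: the rule applied to possible sequences.** In each, CCyR was reached by banding and then followed by FISH. Later assessments are at least 28 days apart.

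| Sequence | Present SAP rule | FISH allowed as one of the pair |
|---|---|---|
| FISH loss, Ph+ marrow, second Ph+ marrow | Event, dated to first marrow | Event, dated to FISH |
| FISH loss, one Ph+ marrow, stops for recorded progression | Event, not dated to FISH | Event, dated to FISH |
| FISH loss, one Ph+ marrow, stops for another recorded reason | Censored | Event, dated to FISH |
| FISH loss, marrow with no Ph+ metaphases | No loss | No loss |

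The third row can arise. Protocol 5.3 lists unsatisfactory response separately from disease progression and refers second-line CP patients to Appendix 5, where loss of CCyR is failure. Protocol 6.3 requires marrow at End of Treatment when the reason is progression or failure. A further marrow at least 28 days later is unlikely to count: SAP 6 limits on-treatment evaluations to 28 days after last dose, and Protocol 6.4 schedules no marrow in follow-up. SAP 8.2.3 considers insufficient clinical response as a possible event for PFS; duration of CCyR has no such provision.

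**Step 2: direction.** In every row the present rule gives the same date, a later date, or censoring in place of an event. The effect is upward or nil.

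**Step 3: dating error per affected patient.** Visits are 13-weekly to Week 52 and 26-weekly after that, with windows of 21 days either side from Week 78 (Protocol Table 1). The SAP converts days to months by dividing by 30.4.

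- Marrow at once: about 0
- Marrow 28 days later: 28/30.4 = 0.9 months
- Marrow at the next 13-week visit: 91/30.4 = 3.0 months
- Marrow at the next 26-week visit: 182/30.4 = 6.0 months
- The same, with FISH 21 days early and marrow 21 days late: (182 + 42)/30.4 = 7.4 months

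**Step 4: what dropped events could do to a Kaplan-Meier rate.** All inputs here are assumptions. Let S be the true 2-year retention, p the share of losses first seen by FISH, and c the share of those that end as censored. If that censoring is unrelated to prognosis, the observed rate is S^(1 - p×c).

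- 10% annual loss, p = 0.5, c = 0.5: S = 0.90² = 0.81, and 0.81^0.75 = 0.854
- 5% annual loss, p = 0.25, c = 0.25: S = 0.95² = 0.9025, and 0.9025^0.9375 = 0.908
- 20% annual loss, p = 1, c = 0.5: S = 0.80² = 0.64, and 0.64^0.5 = 0.80

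A simulation with assessments at 13, 26, 52, 78 weeks and so on after response agrees. Retention is read at week 117 after response:

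| Assumed setting | Reference | Marrow in 4 weeks | Marrow at next visit | Half of FISH losses censored |
|---|---|---|---|---|
| 5% annual loss, p = 0.25 | 90.3% | 90.3% | 90.8% | 91.4% |
| 10% annual loss, p = 0.5 | 81.0% | 81.0% | 83.2% | 85.5% |
| 20% annual loss, p = 1 | 64.1% | 64.1% | 71.6% | 79.7% |

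Over all simulated settings, mean duration restricted to 156 weeks rises by between 0.03 months (33.68 to 33.71) and 3.9 months (27.52 to 31.46).

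**The case against.** The asymmetry may be intended. Protocol 7.1.1.1 reserves the degree of cytogenetic response to marrow banding, FISH is an optional substitute between CCyR and MMR, and a FISH loss sends the patient back to the reference test. An isolated FISH rise may not be a true loss. The safeguards are also real: marrow must resume after a FISH loss, marrow is required at suspected progression or failure, and loss of CCyR is itself a progression criterion for CP, so many FISH losses will end as events anyway. Protocol 9 allows the SAP to modify the protocol's plans and requires an amendment only for major changes to the primary endpoint. Protocol 7.1.1.1 does not say that a mixed FISH and marrow pair qualifies. Finally, SAP 8.2.2 uses Kaplan-Meier only if most responders stay on treatment until progression or loss, so the calculation in Step 4 may not match the analysis performed.

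Most of this stands, and it limits the reach of the point. It supports requiring a banding result in the pair, makes the delay potentially short, and leaves the Kaplan-Meier figures hypothetical. It does not supply the missing criterion. Even with a prompt marrow, the FISH result does not count as the first of the pair, and a second marrow is still needed.

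**Conclusion.** The gap is in the text: a FISH result of 1% or more can neither start nor confirm a loss of CCyR, although FISH may be the monitoring test. Duration of CCyR can be overstated for patients whose loss is first seen by FISH; this gap does not understate it. The dating error runs from near zero with prompt marrow to about 6 months (7.4 with windows) if marrow waits for the next 6-monthly visit. The effect on the cohort estimates cannot be derived, because the documents give neither the share followed by FISH nor a loss rate.

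A reader might infer four stronger things that the documents do not support:

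- That the endpoint ends only on marrow metaphases. Progression and on-treatment death also end it.
- That the durations will be too long by a known amount. The bias is possible and may be negligible.
- That the SAP breaches the protocol. It is narrower than the protocol's wording, which Protocol 9 permits.
- That duration of MCyR needs the same FISH criterion. FISH of 1% or more does not show loss of MCyR, which includes PCyR with up to 35% Ph+ metaphases.

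A change is worth making for a secondary endpoint because it is specific and cheap.

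**What to change.** In SAP 6.1, for duration of CCyR only, define confirmed loss as two consecutive assessments at least 28 days apart. Each is either banding with more than 0 Ph+ metaphases (at least 20 analysed) or FISH with at least 1% positive nuclei (at least 200 analysed). At least one must be by banding, and the loss is dated to the first of the pair. Progression and on-treatment death remain events. Keep the present metaphase-only rule as a sensitivity analysis, so that the difference is visible.

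Do not carry the FISH criterion to the exploratory duration of MCyR. SAP 6.1 now makes it follow the CCyR rules; give it a separate banding-based loss rule consistent with the MCyR definition in Appendix 2.

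The cost is a wording change and one revised derivation for duration of CCyR, plus the separate MCyR rule. FISH results used to follow CCyR are already study data, so no new assessments are needed. The downside is that reported durations of CCyR become slightly shorter.
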